6.1 RELATIONSHIP

The relationship or association of the AE to study product will be characterized by the following categories:

Not related:

- There is no temporal relationship between the study product/treatment and the event, which makes a causal relationship clearly and incontrovertibly due to extraneous causes, e.g. not related to study product.
- Other factors, such as concurrent illness, progression or expression of a disease, or a reaction to a concomitant medication are a more likely the cause of the event. It is improbable that the study product caused the AE.

Possibly related:

• The AE cannot be fully explained by other causes, and it is possible that the study product caused the event.

Related:

- A reasonable temporal association exists between the AE and the study product, and based upon the investigators clinical experience, the association of the AE with the study product treatment seems probable.
- A definite or certain temporal association exists between the AE and study product, and based upon the Investigator's clinical experience, the association of the AE with study product seems definite or certain.

6.2 SERIOUS ADVERSE EVENTS

Serious Adverse Events are those Adverse Events that are:

- Are life-threatening,
- Are fatal,
- Result in inpatient hospitalization or prolongation of a hospitalization,
- Result in persistent or significant disability/incapacity, or
- Result in congenital anomaly or birth defect.

6.3 ANTICIPATED AND UNANTICIPATED ADVERSE DEVICE EFFECTS

6.3.1 Anticipated Adverse Events

Anticipated adverse events related to ventral hernia repair include post- operative surgical site events such as ileus, deep or superficial wound infection, seroma, hematoma, wound dehiscence, skin necrosis, fistulae and recurrent hernia. A comprehensive list of these events can be found in a patient information brochure at the American College of surgery website; (http://www.facs.org/public info/operation/brochures/ventral hernia.pdf), see Appendix Although anticipated, should these events occur in subjects enrolled in this study, they are considered Adverse Events and should be noted in the eCRF.

In addition to those events listed above, there are other anticipated adverse device effects that include failure of the product to incorporate, rupture of the OviTex® Permanent 1S reinforced bioscaffold sheet or dehiscence of the product, mesh infection, bowel obstructions from adhesions or other mesh complications. These events, although possible and therefore defined as anticipated, are considered to be rare occurrences.

6.3.2 Unanticipated Adverse Device Effects (UADEs)

As per 21 CFR 812.3, Unanticipated adverse device effects are those effects, which have a serious adverse effect on health or safety or any life-threatening problem or death caused by, or associated with a device, if that effect, problem or death was not previously identified in nature, severity, or degree of incidence.

In this study all SAEs as defined in Section 6.2 above and adverse events which occur that are not identified will be considered Unanticipated Device Effects and will be reported to the Sponsor as described in Section 6.4.

6.4 INVESTIGATOR REPORTING REQUIREMENTS

6.4.1 Reporting Serious Adverse Events

In addition to notation in the CRF, all SAEs will also require completion of a separate reporting form for submission to the Sponsor through Day 90. All Serious Adverse Events will be reported to TELA Bio within 24 hours of the Investigator's first awareness of their occurrence. Following the Day 90 visit, only SAEs considered by the Investigator to be "Related or "Possibly Related" to the study product will require completion of the additional reporting form for submission to the Sponsor. Conversely, following the Day 90 visit, it will no longer be necessary to complete the separate reporting form for those SAEs that the Investigator determines to be "Unrelated" to the OviTex mesh.

6.4.2 Reporting Unanticipated Adverse Device Effects (UADEs)

Unanticipated adverse device effects (UADEs) are those that in nature, severity or degree of incidence differ from the list of anticipated adverse events above. UADEs will be reported to the Sponsor within 24 hours of the Investigator's first awareness of their occurrence.

6.5 SERIOUS ADVERSE EVENT AND UADE REVIEW

Reported SAEs and UADEs will be reviewed and investigated per TELA Bio Operating Procedures. When considered appropriate, TELA Bio will notify pertinent regulatory bodies and all Investigators within 10 working days of TELA Bio's receipt of notification of the event. It is the Investigators responsibility to notify their respective IRBs.

6.6 COMPLAINTS

Any deficiencies related to the identity, quality, durability, reliability, safety, effectiveness or performance of OviTex® Permanent 1S reinforced bioscaffold, but which are not Adverse Events, will be promptly reported to the Sponsor's Customer Service Department.

7 STATISTICAL CONSIDERATIONS AND DATA MANAGEMENT

7.1 SAMPLE SIZE

A sample size of up to 100 subjects is planned for this study. This is a sample of convenience and is estimated to be sufficient to allow assessment of clinical performance in this patient population.

7.2 STATISTICAL METHODS

Statistical methods will be carried out in accordance with the Statistical Analysis Plan (SAP) developed for this study.

The majority of data will be expressed as descriptive statistics. A p-value of less than or equal to 0.05 will be considered statistically significant. Any confidence bounds will show two-sided 95% confidence interval limits. Categorical variables will be summarized by number and percent. Continuous variables will be summarized by total number (N), mean, standard deviation, median, min and max. It is anticipated that the data will be evaluated using standard parametric and non-parametric procedures. Analyses of particular interest will be:

1. Correlation of rate of surgical site wound infection to SSI wound classification, number of previous repairs and pre-morbid conditions.

- 2. Correlation of surgical site occurrences or wound related events to re-herniation, BMI, number of previous abdominal.
- 3. Correlation of number of previous repairs with true hernia recurrence
- 4. Correlation of a visible bulge at hernia repair site with true hernia recurrence
- 5. Correlation of subject abdominal wall function and QoL with bulging at the hernia repair site and hernia recurrence rates.

The primary and secondary endpoints of this study will be also be compared to the clinical outcomes reported for other prospective studies in the literature. The results will be compared for the group as a whole, and, if the numbers will allow this, for subgroups of subjects exhibiting similar baseline characteristics, such as size of the hernia, co-morbid conditions, number of previous abdominal procedures etc.

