A baseline visit will be performed prior to the ventral hernia repair and will include assessment of the subject's medical history, physical exam and pre-operative instructions. The subjects will also complete baseline Quality of Life (QOL) Surveys, one of which will be a disease specific assessment (HerQLes) and the other a standard measure of health outcomes (EQ-5D)

On the day of surgery, repair of the ventral hernia will occur using OviTex® Permanent 1S reinforced bioscaffold to reinforce the repaired hernia site. Perioperative data will be collected, including the anatomical placement of the mesh and fixation methods. During the course of hospitalization the patient will be assessed for incidence of early post-operative surgical site wound events and complications including the nature and severity of the complications, all necessary medical interventions and/or re-operations.

On the day of hospital discharge, surgical site occurrences or wound related events (e.g. infections, hematomas, seromas, wound dehiscence) noted at the hernia repair site and the occurrence of other early post-operative complications (e.g. ileus, bowel obstruction, fistulae) will be assessed.

At post-operative days 30 and 90, surgical site occurrences or wound related events (e.g. infections, hematomas, seromas, wound dehiscence) noted at the hernia repair site will be assessed. If a clinically significant hernia is suspected e.g. bulging noted at the hernia site, it will be confirmed via diagnostic imaging with a CT scan. The occurrence of other post-operative complications (e.g. ileus, bowel obstruction, fistulae) will be also assessed. Disease specific and general Quality of Life (QoL) surveys (HerQLes and EQ-5D), a pain scale and a subject/surgeon satisfaction assessment will also be administered.

At post-operative months 12 and 24, late surgical site occurrences or wound related events (e.g. infections, hematomas, seromas, wound dehiscence, bulging) noted at the hernia repair site will be assessed. If a clinically significant hernia is suspected e.g. bulging noted at the hernia site, it will be confirmed via diagnostic imaging with a CT scan. The occurrence of other late post-operative complications (e.g. ileus, bowel obstruction, fistulae) will also be assessed. Disease specific and general Quality of Life (QoL) surveys (HerQLes and EQ-5D), a pain scale and a subject/surgeon satisfaction assessment will also be administered.

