2.2 PRIMARY AND SECONDARY ENDPOINTS

2.2.1 Primary Endpoints

1. Incidence of early post-operative surgical site occurrences or wound related events (e.g. - ileus, deep or superficial wound infection, seroma, hematoma, wound dehiscence, skin necrosis, fistulae) noted at the hernia repair site and occurring within the first three months

of the ventral hernia repair.

2. Incidence of other early post-operative complications (e.g. ileus, bowel obstruction, fistula) occurring within the first three months of the ventral hernia repair.

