2.2.2 Secondary Endpoints

- Incidence of late post-operative surgical site occurrences or wound related events (e.g. ileus, deep or superficial wound infection, seroma, hematoma, wound dehiscence, skin necrosis, fistulae, bulging) noted at the hernia repair site and occurring > 3 months after index surgery.
- 2. Incidence of other late post-operative complications (e.g. ileus, bowel obstruction, fistula) occurring > 3 months after index surgery.
- 3. Patient Reported Outcomes (QoL and pain assessments).
- 4. True hernia recurrence at the site of surgery at post-operative day 90 and 12 and 24 months.

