3.2.3 Discharge

On the day of hospital discharge, the following will be collected:

- Length of Stay, including number of days hospitalized prior to repair and following surgery, the number of days in ICU, step down and regular ward.
- Number of drains still in place, drain volume and duration.
- Any early surgical site occurrences (infections, seroma, hematoma, wound dehiscence)
 or wound related events noted at the hernia repair site.
- Any other early post-operative complications (ileus, fistulae).

3.3 POST-OPERATIVE DAYS 30 AND 90

At post-operative days 30 and 90, the following procedures will be completed:

- Number of drains still in place, drain volume and duration.
- Assessment of any surgical site occurrences or wound related events (infections, seromas, hematoma, wound dehiscence) noted at the hernia repair site.
- A relevant physical examination to evaluate hernia repair. If there is any suspicion of a recurrent hernia e.g. bulging noted at the repair site, an abdominal CT scan will be performed to confirm the clinical diagnosis. If it is determined that it is clinically necessary to repair the hernia recurrence during the study period, those subjects will complete their participation in the study at the time of that repair
- Assessment of any other post-operative complications (ileus, fistulae).
- Assessment of disease specific and general Quality of Life (QoL) surveys e.g. EQ-5D and HerQLes, (See Appendix 1).
- Subject and Surgeon satisfaction assessment of hernia repair (See Appendix 5).
- Subject assessment of post-operative pain as measured by the Pain Visual Analog Scale ((VAS) See Appendix 5).

3.4 POST-OPERATIVE MONTHS 12 AND 24

The following activities will be performed at months 12 and 24 of Study period visit:

- Assessment of any late surgical site occurrences or wound related events (e.g. infections, seromas, hematoma, wound dehiscence, bulging) noted at the hernia repair site.
- A relevant physical examination to evaluate hernia repair. If there is any suspicion of a recurrent hernia e.g. bulging noted at the repair site, an abdominal CT scan will be performed to confirm the clinical diagnosis. If it is determined that it is clinically necessary to repair the hernia recurrence during the study period, those subjects will complete their participation in the study at the time of that repair.

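### Bulging counts as a late surgical site occurrence and is also the named sign leading to a recurrence diagnosis, so the planned correlation of site occurrences with re-herniation is biased upward

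*Combined protocol and SAP*

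**What the plan says.** Secondary endpoint 1 (Section 2.2.2) ends its list of late site occurrences with "wound dehiscence, skin necrosis, fistulae, bulging) noted at the hernia repair site and occurring > 3 months after index surgery". Section 3.4 has the same item assessed at Months 12 and 24: "Assessment of any late surgical site occurrences or wound related events (e.g. infections, seromas, hematoma, wound dehiscence, bulging) noted at the hernia repair site".

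The next bullet in Section 3.4, and the matching bullet in Section 3.3, give the route to a recurrence diagnosis: "If there is any suspicion of a recurrent hernia e.g. bulging noted at the repair site, an abdominal CT scan will be performed". The Study Overview says the same: "If a clinically significant hernia is suspected e.g. bulging noted at the hernia site, it will be confirmed via diagnostic imaging with a CT scan". Bulging is the only sign named in any of these places.

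Recurrence is a separate endpoint, secondary endpoint 4: "True hernia recurrence at the site of surgery at post-operative day 90 and 12 and 24 months".

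Section 7.2 then lists analysis 2, "Correlation of surgical site occurrences or wound related events to re-herniation, BMI, number of previous abdominal", and separately analysis 4, "Correlation of a visible bulge at hernia repair site with true hernia recurrence". Analysis 2 has no early/late restriction and does not exclude bulging. The early definition in Section 2.2.1 does not list bulging: "seroma, hematoma, wound dehiscence, skin necrosis, fistulae) noted at the hernia repair site and occurring within the first three months". Section 6.3.1 goes further than Section 2.2.2 and puts recurrent hernia itself among the anticipated surgical site events.

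**The concern.** One physical finding can supply both variables in analysis 2. A subject whose recurrence shows as a bulge at Month 12 is a late site occurrence because of the bulge, and a recurrence once CT confirms it. The overlap is one of definition and would remain if every subject had a CT scan.

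What is at stake is the reading of analysis 2. A positive result would naturally be taken to mean that infection, seroma, dehiscence and similar events go with re-herniation, yet it could arise with no such relation. Section 7.2 sets p ≤ 0.05 as significant, so the result could be reported as a finding. The late site-occurrence rate also contains some recurrences, and a reader cannot tell how many.

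**Working it through.** **The plan's own figure.** There is none to reproduce. Section 7.1 describes up to 100 subjects as a sample of convenience, and no correlation or power is stated for analysis 2.

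**Inputs.** From the documents: N = 100 (Section 7.1), p ≤ 0.05 (Section 7.2), and a reported recurrence range of 2.7% to 62% (Section 1.1). Everything else is assumed:

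- r, recurrence rate: 2.7%, 5%, 10%
- p, site occurrences other than bulging, independent of recurrence: 10% to 30%
- s, share of recurrences that show a bulge: 80% to 100%, with 50% as a less favourable case
- f, bulge without recurrence (CT-negative): 5%

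**Formulas.**

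- P(occurrence | recurrence) = 1 − (1 − s)(1 − p)
- P(occurrence | no recurrence) = 1 − (1 − f)(1 − p)
- Difference = (1 − p)(s − f)
- Overall rate m = r·P(occurrence | recurrence) + (1 − r)·P(occurrence | no recurrence)
- phi = difference × √[r(1 − r) / (m(1 − m))]

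The difference is positive whenever s > f, that is, whenever bulging is commoner in recurrent than in non-recurrent subjects.

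**Worked case** (r = 5%, p = 10%, s = 80%, f = 5%). The two probabilities are 1 − 0.2 × 0.9 = 0.82 and 1 − 0.95 × 0.9 = 0.145. Then m = 0.05 × 0.82 + 0.95 × 0.145 = 0.179, and phi = 0.675 × √[0.0475 / (0.179 × 0.821)] = 0.38. With s = 100%, phi is 0.48.

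**Chance of a significant result** (two-sided Fisher exact test, simulated, no true association between other wound events and recurrence, f = 5%):

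| r | p | s | phi | p ≤ 0.05 |
|---|---|---|---|---|
| 2.7% | 10% | 80-100% | 0.30-0.37 | about 55-75% |
| 5% | 10% | 80-100% | 0.38-0.48 | about 82-97% |
| 10% | 10% | 80-100% | 0.50-0.61 | about 98-99.9% |
| 2.7% | 30% | 80% | 0.18 | about 28% |
| 5% | 30% | 80% | 0.24 | about 59% |
| 5% | 20% | 50% | 0.18 | about 33-35% |
| 10% | 20% | 50% | 0.24 | about 59% |

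With bulging out of the variable (s = f = 0), phi is 0 and the rate is about 2%, as expected of a conservative exact test.

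**Effect on the late site-occurrence rate** (p = 10%). Recurrence bulges add r·s·(1 − p):

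- at r = 5%, 0.05 × 0.8 × 0.9 = 3.6 points, up to 0.05 × 1 × 0.9 = 4.5 points;
- at r = 10%, 7.2 to 9.0 points.

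CT-negative bulges add (1 − r)·f·(1 − p): 0.95 × 0.05 × 0.9 = 4.3 points at r = 5%, and 0.90 × 0.05 × 0.9 = 4.1 points at r = 10%.

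**The case against.** **Bulging may mean laxity only.** Section 1.1 lists laxity separately from true recurrence. If a CT-confirmed bulge is reclassified as recurrence and leaves the site-occurrence count, the upward bias disappears. This is the strongest counter-argument, but no endpoint rule adopts that reading, and analysis 4 implies that bulges are recorded whether or not recurrence follows. The reading would also leave a smaller bias the other way. With confirmed bulges removed and CT-negative ones kept, the difference becomes −(1 − p)f = −0.9 × 0.05 = −0.045. Leaving bulging out of analysis 2 removes the problem under either reading.

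**A rule may exist elsewhere.** Section 7.2 defers to a statistical analysis plan. The supplied text contains no such rule. If one exists, it would settle the point.

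**It is exploratory.** This stands as a limit on importance. Analysis 2 is one of five correlations in a mostly descriptive single-arm study, and no primary endpoint is affected. Analysis 4 already isolates bulge against recurrence, but that is also why analysis 2 adds information only if it reflects the other wound events.

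**Stronger readings that the documents do not support.**

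- A reader might infer that every recurrence is counted twice. Bulging is listed only for late occurrences and is given as an example of a sign, so the overlap covers late recurrences that present as a bulge.
- A reader might infer that a strong or significant correlation is guaranteed. Only the upward direction is robust. Pooling early occurrences, whose definition does not list bulging, dilutes the effect, as the 30% rows show.
- A reader might attribute the whole rise in the late rate to recurrences. At 5% recurrence about half comes from CT-negative bulges, which Section 2.2.2 counts on purpose.
- A reader might conclude that comparison with the literature is distorted because published rates omit bulging. The documents do not say what those studies counted.

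**Conclusion.** The concern holds as an upward bias in analysis 2 of Section 7.2, for late recurrences that present as a bulge. It arises because the supplied text does not say how a CT-confirmed bulge is counted. The direction requires only that bulging be commoner in recurrent than in non-recurrent subjects. The size rests on assumed rates: across the settings tabulated, a spurious significant result occurs in about 28% to 99.9% of trials, against about 2% with bulging removed. Recurrence bulges alone add about 4 points to the late site-occurrence rate at 5% recurrence and 7 to 9 points at 10%. The point should be fixed because the change is nearly free, but it does not threaten the primary endpoints.

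**What to change.** **Section 7.2, analysis 2.** Define the site-occurrence variable without bulging and, given Section 6.3.1, without recurrent hernia. Use the same time window for all subjects, for example occurrences within the first three months. Leave bulge against recurrence to analysis 4.

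Counting only events that precede the first suspicion of recurrence is a tempting alternative, but it shortens the window for recurrent subjects alone. In a check it pushed the correlation negative, by about 0.05 to 0.08. A common window avoids this.

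**Section 2.2.2, endpoint 1.** Keep the definition; bulging is a deliberate outcome, since Section 1.2 hypothesises that these scaffolds are not prone to it. Add a line reporting late site occurrences with and without bulging, and split bulging into CT-confirmed recurrence and CT-negative bulge.

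**Cost.** The change is to wording, with fewer events in analysis 2 and one extra table line. With a three-month window, late wound events also drop out of analysis 2. Bulging and CT confirmation are already part of the late visits in Section 3.4, so no new procedure is needed. The case report form was not available, so the sponsor should confirm that bulging is recorded as its own item.

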1 INTRODUCTION

1.1 BACKGROUND

Meshes are indicated to reinforce absent or weakened soft tissue. Their main clinical application is found in hernias and abdominal wall defects. [1-3] In these diagnoses, the fascia underlying the abdominal muscles (rectus abdominus, transverse, internal and external obliques) exhibits a defect. The fascia is a layer of dense organized connective tissue that resists tension forces. It is comprised of closely packed bundles of organized collagen fibers, produced by the resident fibroblasts. [4, 5]

A defect in the fascia allows abdominal contents, e.g. the viscera, to migrate or 'herniate' to a position outside the abdominal cavity, under the skin. Ventral hernias are common and are often the result of previous abdominal surgeries where the sutured fascia ultimately fails (incisional hernia). [6, 7] The term 'abdominal wall defect' is reserved for situations where a substantial section of the fascia is missing, and surgical repair is challenging. This can be caused by failed previous surgeries, infections, trauma and other causes. Many subjects with ventral hernias or abdominal wall defects suffer from co-morbid conditions that can have a negative impact on healing, such as obesity, diabetes, COPD, steroid use, or the presence of a stoma, [8] which may add to the complexity of the surgical repair and recovery. Reported recurrence rates after ventral hernia repair range from 2.7% to 62%. [2] [9-13]

The goal for surgical repair of these ventral hernias is to obtain a tension-free primary closure of the defect in [1-3] the fascia, although this is not always possible. Techniques used to create more 'real estate' to achieve this goal, such as component separation, result in an increased surface area, but an overall thinner, and thus potentially weaker, abdominal wall. [1, 14] To reinforce the abdominal wall, many hernia surgeries include the use of a mesh. In cases where primary closure has been achieved, the mesh is used to reinforce the fascia and is placed either on top or below the newly constructed abdominal wall. e.g. 'onlay' or 'underlay'.[15] In cases

where primary closure cannot be achieved meshes are used to bridge the remaining defect, e.g. 'inlay'.[16]

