2.3.1 Rationale for the OviTex® Permanent 1S reinforced bioscaffold study

The purpose of the OviTex® Permanent 1S reinforced bioscaffold Study is to provide prospective data on the early post- operative clinical course and the true hernia recurrence rates in the repair of ventral hernias. Data relating to subjects with similar baseline characteristics will be correlated and compared to (prospective) published data where applicable.

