2.7 INCLUSION CRITERIA

2.7.1 Inclusion Criteria at Screening: Visit 1

- Subject suffers from an uncomplicated ventral hernia that requires surgical repair (open, laparoscopic or robotic) with the use of an implant to reinforce or replace weakened or missing tissue.
- 2. The size of the implant needed for repair is expected to be 18 x 22 cm, 20 x 20 cm or less.
- 3. Subject meets CDC/SSI Wound Classification Class I (Clean), Class II (Clean-Contaminated) or Class III (Contaminated) criteria.
- 4. Subject is willing and able to sign an informed consent for the study and has signed the IRB approved Informed Consent form for this study.

- 5. Subject is able to complete Quality of Life (QoL) and pain Questionnaires.
- 6. Subject is at least 18 years old, (or considered an adult per state law).
- 7. Subject is able to participate fully in, and for the full duration of, the study.

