3.2.2 Intraoperative

On the day of surgery, definitive repair of the ventral hernia site will be performed with an OviTex® Permanent 1S reinforced bioscaffold implant. The Investigator will use the study product on a first-to-expire basis. Investigators will follow their individual Institutional guidelines for their standard surgical preparation regimen. During the index surgery, the following perioperative components will be collected:

- Type of approach (Laparoscopic versus Open)
- Actual size of defect (length, width, cm²)
- Product item and lot-serial number used

- Size of implant used in surgery (final mesh dimensions after any trimming)
- Location of implant (onlay, retrorectus, extraperitoneal, intraperitoneal or inlay/bridging)
- Operative data
 - o Component separation (anterior or posterior)
 - Fixation method (suture type and size)
 - o Number of drain(s) placed, drain volume and duration
 - Rectus muscle condition
 - o Presence or absence of adhesions
 - Any concomitant procedures
 - Iatrogenic injury
 - o Blood loss
 - Skin closure (complete restoration of abdominal wall and primary skin closure)
 - Operative time (time of first cut to last suture)
- All subjects will be assessed for intraoperative complications.
- Using a Likert scale, surgeons will be asked to provide their subjective assessment on the mesh handling characteristics as defined by ease of placement and ease of securing OviTex® Permanent 1S reinforced bioscaffold implant (See Appendix 3).

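### The same-or-lower comparison with published studies names no operative factor, so a difference in operation mix could be credited to the mesh or could hide its effect

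*Combined protocol and SAP*

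**What the plan says.** Section 2.1 states a comparative aim: early complications and true recurrences no more frequent than in prospective reports of other meshes. There is no concurrent control. Section 2.3.1 sets the basis of comparison: "Data relating to subjects with similar baseline characteristics will be correlated and compared to (prospective) published data where applicable". Section 7.2 compares the endpoints with other prospective studies for the group as a whole. If numbers permit, it does so also "for subgroups of subjects exhibiting similar baseline characteristics, such as size of the hernia, co-morbid conditions, number of previous abdominal procedures etc". Section 7.2 also sets a significance level: "A p-value of less than or equal to 0.05 will be considered statistically significant".

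The operation is left open. Under 2.7.1 the hernia "requires surgical repair (open, laparoscopic or robotic) with the use of an implant". Section 3.2.2 records "Location of implant (onlay, retrorectus, extraperitoneal, intraperitoneal or inlay/bridging" and anterior or posterior component separation. None of these appears in the literature comparison or in the five analyses of particular interest in 7.2.

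The background (1.1) treats technique as relevant. It describes methods "such as component separation, result in an increased surface area, but an overall thinner, and thus potentially weaker, abdominal wall", and it separates mesh that reinforces a closed defect from mesh that bridges an open one.

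**The concern.** With a literature control, the conclusion is only as good as the definition of comparability. Two series with the same hernia sizes, co-morbidities and surgical histories can still differ in early wound events and recurrence because the operations differed. Read as written, the plan would attribute that difference to the mesh. This affects both primary endpoints and the recurrence endpoint. It would remain even if every comparator were a well-chosen ventral hernia series.

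**Working it through.** **The plan's own figure.** Section 7.1 says: "A sample size of up to 100 subjects is planned for this study" and "This is a sample of convenience and is estimated to be sufficient to allow assessment of clinical performance in this patient population". It gives no reference rate, margin or power, so there is no calculation to reproduce.

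**Inputs.** From the documents: n = 100 (7.1) and two-sided 95% limits (7.2). Assumed, because the documents give nothing by operation: three-month wound-event rates by approach, the minimally invasive (MI) share in the trial and in the comparator, and a published rate treated as fixed. The device effect is set to zero. The plan states no decision rule, so a result is called lower when the exact (Clopper-Pearson) 95% upper limit falls below the published rate.

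**Formula.** Rate = open rate × (1 − MI share) + MI rate × MI share, applied to the trial and to the comparator.

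**Assumed rates of 30% open and 10% MI**

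- All-open comparator: published rate 30%. Twenty events in 100 give an upper limit of 29.2% and 21 give 30.3%, so the result is lower at 20 events or fewer.
- Comparator 40% MI: 0.30 × 0.60 + 0.10 × 0.40 = 22%. Thirteen events give 21.2% and 14 give 22.4%, so the cut-off is 13.
- Trial 50% MI: 0.30 × 0.50 + 0.10 × 0.50 = 20%. Trial 60% MI: 0.30 × 0.40 + 0.10 × 0.60 = 18%.

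| Comparator | Trial MI share | True rates, trial vs published | Chance of a false lower result |
|---|---|---|---|
| all open | 0% (equal mix) | 30% vs 30% | 1.6% |
| all open | 25% | 25% vs 30% | 15% |
| all open | 50% | 20% vs 30% | 56% |
| all open | 75% | 15% vs 30% | 93% |
| 40% MI | 40% (equal mix) | 22% vs 22% | 1.6% |
| 40% MI | 50% | 20% vs 22% | 4.7% |
| 40% MI | 60% | 18% vs 22% | 11.8% |

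**Assumed rates of 25% open and 15% MI.** Against an all-open comparator the chances are 2.1%, 7%, 19% and 41% at MI shares of 0, 25, 50 and 75%. Against a 40% MI comparator (published rate 21%) they are 1.4%, 2.5% and 4.3% at shares of 40, 50 and 60%.

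**Opposite direction.** At 30% and 10%, a trial with 25% MI against a comparator with 40% MI has a true rate of 25% against 22%. The device then looks 3 points worse with no effect of its own.

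**How far the data can be split.** Three approaches × five mesh locations × three component-separation levels (none, anterior, posterior) make 45 cells, and 100/45 is about 2.2 subjects per cell. With the two approaches listed in 3.2.2 there are 30 cells, about 3.3 each. One-factor strata are feasible but imprecise. At an observed 20%, the exact 95% interval is 12.7–29.2% for n=100, 10.0–33.7% for n=50 and 5.7–43.7% for n=20.

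**The case against.** A reader might infer that the plan matches on patient factors and shuts technique out. The text does not support that. Section 7.2 matches on nothing: its first comparison is unadjusted, the subgroups are conditional on numbers, and the list of factors is illustrative and open-ended. Section 3.1 determines surgical approach at the baseline visit, so approach could count as a baseline characteristic. It is unnamed, not excluded. That reading does not rescue bridging, mesh location or component separation, which are known only at surgery, and an open-ended list is not prespecification.

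Section 7.2 also defers to a SAP, but the reviewed file contains no SAP text on this point. If the SAP covers it, aligning the protocol costs little.

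Most data will be summarised descriptively, and the comparison also lacks named comparators, reference rates and a margin, so this point is one part of a wider gap. That is true. But 2.1 says the study is designed to demonstrate the result, and operation mix would still confound the comparison after those items were supplied.

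Finally, the large probabilities need an all-open comparator, and crossing every operative factor is not feasible at 100 subjects. Both points stand and limit the conclusion and the fix.

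**Conclusion.** The point holds in this form: as written, the comparison cannot separate the device from the mix of operations, and the variables needed to reduce the problem are largely collected already. It should be corrected before the literature comparison is made.

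It would be wrong to infer that a false favourable result is likely, or that the bias favours the device. Under 30%/10% rates and a half minimally invasive trial, the chance runs from 4.7% to 56% depending only on whether the comparator is 40% minimally invasive or all open. Under 25%/15% rates it runs from 2.5% to 19%. All rates and mixes are assumptions, and the sign reverses if the trial has the larger share of higher-risk operations. The calculation covers approach and wound events only. Nothing was computed for bridging, mesh location, component separation or recurrence, where the case rests on the protocol's own account of technique in 1.1.

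**What to change.** - In 2.3.1 and 7.2, define comparability by baseline and operative characteristics.
- Prespecify two one-factor breakdowns, in this order: approach (open versus laparoscopic/robotic), then bridged versus reinforced repair.
- Compare each stratum with published series of the same type, or weight the trial's stratum rates to the mix the published series reports: weighted rate = Σ (published share × trial stratum rate). In the example above, a half minimally invasive trial weighted to a 40% minimally invasive series gives 0.60 × 30% + 0.40 × 10% = 22%, which equals the published rate and removes the spurious 2 points.
- Report mesh location and component separation descriptively, without cross-classifying.
- Where a published series does not report its mix, show the comparison descriptively and draw no same-or-lower conclusion about the device from it.
- Add robotic to the approach field in 3.2.2, which lists only laparoscopic and open, so that it agrees with 2.7.1.

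Cost: wording in 2.3.1, 7.2 and the SAP, and one case report form category. No new visits or subjects are needed. Intervals within strata will be wider (10.0–33.7% for n=50 at a 20% rate), and some published series will drop out of the inferential comparison.
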